#### 2.4.3 Primary Effectiveness Analysis

Responder rate for each treatment based on the GDS, as assessed live by the Treating Investigator at 9 months after baseline, will be the primary effectiveness endpoint. A responder will be defined as a subject with at least 1 grade improvement from baseline. The response rate will be calculated and presented with the 95% confidence intervals (calculated via Clopper-Pearson) for each treatment group and overall.

[figure not shown]

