Vascular occlusion resulting in ischemia/necrosis and visual disturbances including blindness have been reported following injection of any soft tissue filler in the face especially in the nose, glabella, periorbital areas, nasolabial folds and cheek, with a time to onset ranging from immediate to a few weeks following injection. For intravascular complications or embolic events, the treating physician should provide prompt medical attention and follow relevant clinical practice guidelines for handling these symptoms. (16) The treating physician should also review the Intravascular Treatment Protocol (17) provided separately as a supportive tool.

Investigators will be carefully selected to assure proper device implantation and minimization of study risk and Investigators must meet the following criteria:

Lidocaine can, in rare cases, elicit allergic reactions, and therefore subjects with a known allergy or hypersensitivity to local anesthetics should not be included in the study.

Additional information about reported AEs and anticipated risks are included in the study Instructions for use (IFU) (18) and the ROPI (15).

Doc id
MA-50966

2022-06-13 07:02

Stopping rules for the study are outlined in Section 7.11.

The potential risks related to treatment with Sculptra for correction of wrinkles in the décolletage area have been assessed and evaluated in accordance with requirements in the ISO 14971 standard and the Sponsor's established risk management procedures.

STUDY OBJECTIVES, ENDPOINTS AND HYPOTHESIS

Effectiveness objectives and endpoints

Primary Effectiveness objective:

To evaluate the effectiveness of *Sculptra* for correction of wrinkles in the décolletage area.

Secondary Effectiveness objectives:

To evaluate the effectiveness of *Sculptra* for correction of wrinkles in the décolletage area.

To compare the effectiveness of Sculptra for correction of wrinkles in the décolletage area between the two treatment groups.

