9.4 Effectiveness analysis

Continuous endpoints will be summarized using descriptive statistics, e.g. mean, median, SD, minimum and maximum values. Categorical endpoints will be presented in frequency tables with number and percentage of observations for each level.

Responder rate regarding GAIS and GDS will be presented together with a 95% confidence interval (based on the binomial distribution). The difference in responder rate regarding GAIS and GDS will be calculated between the two groups presented together with a 95% confidence interval.

No adjustment to the level of significance will be performed; p-values obtained for any endpoint other than the primary will only be provided for ease of interpretation of the results.

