## 1.2 Study Objectives and Endpoints

### 1.2.1 Primary Effectiveness Objective and Endpoint

The primary objective of the study is to evaluate the effectiveness of *Sculptra* for correction of wrinkles in the décolletage area. The primary endpoint is the percentage of responders, defined by at least one grade improvement from baseline, on the GDS, as assessed live by the Treating Investigator, at Month 9 for each treatment group.

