### 1.2.2 Secondary Effectiveness Objectives and Endpoints

To evaluate the effectiveness of *Sculptra* for correction of wrinkles in the décolletage area the following endpoints will be used:

1. Percentage of responders, defined by at least one grade improvement from baseline, on the GDS, as assessed live by the Treating Investigator, at Month 6.
2. Percentage of responders, defined by having at least “Improved” (improved, much improved or very much improved) according to the Global Aesthetic Improvement Scale (GAIS), as assessed by the subject and the Treating Investigator separately, at Month 6 and 9.

CCI

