#### 2.4.4 Secondary Effectiveness Analysis

- (i) To evaluate the effectiveness of *Sculptra* for correction of wrinkles in the décolletage area, the following will be presented.

[figure not shown]
The percentage of responders on the GDS as assessed live by the Treating Investigator at 6 months after baseline will be presented along with the 95% confidence intervals (calculated via Clopper-Pearson) for each treatment group and overall.

The response rates based on the GAIS as assessed by the investigator and the subject, respectively, at each visit will be calculated and presented along with their 95% confidence intervals (calculated via Clopper-Pearson) for each treatment group and overall. A bar plot of the percentage of responders (at least “Improved”) by visit also will be produced for each evaluator type (investigator and subject) and presented by treatment group and overall. For the GAIS, response rate is defined as a subject with a rating of at least “improved”.

CCI

 GALDERMA EST. 1981	Title 43USSA2112 Statistical Analysis Plan - Sculptra Decolletage US Pilot	Doc id MA-55694
---	--	---------------------------

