#### 2.4.6 Subgroup Analyses

All data will be summarized by treatment group injection volume: 8 vs 17 mL.

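### Does the SAP drop the between-group difference in responder rates that the protocol plans, or leave its confidence interval undefined?

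*SAP*

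**What the plan says.** Protocol section 9.4, after the per-group responder rates, states: "The difference in responder rate regarding GAIS and GDS will be calculated between the two groups presented together with a 95% confidence interval". Section 2.1 lists, under the secondary effectiveness objectives, "To compare the effectiveness of Sculptra for correction of wrinkles in the décolletage area between the two treatment groups".

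The SAP is written group by group. Section 1.2.1 sets the primary endpoint "as assessed live by the Treating Investigator, at Month 9 for each treatment group", and section 2.4.3 says "The response rate will be calculated and presented with the 95% confidence intervals (calculated via Clopper-Pearson) for each treatment group and overall". In section 2.4.4 the GDS responder rate "at 6 months after baseline will be presented along with the 95% confidence intervals (calculated via Clopper-Pearson) for each treatment group and overall", and the GAIS rates "at each visit will be calculated and presented along with their 95% confidence intervals (calculated via Clopper-Pearson) for each treatment group and overall". The readable objective in section 1.2.2 is the evaluative one only ("for correction of wrinkles in the décolletage area the following endpoints will be used"). Section 2.4.6 adds "All data will be summarized by treatment group injection volume: 8 vs 17 mL", which gives summaries by group, not a contrast.

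Three further provisions bear on the reading. SAP section 2.1 gives the SAP precedence over the protocol's statistical sections where the two differ. Section 2.8 declares no changes to the protocol's planned analysis. Section 2.1.2 fixes two-sided 95% intervals.

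**The concern.** Protocol section 1.1 says the 18 mL total volume is to be compared with the labelled 9 mL, and section 1.2 says the data will support a pivotal study. The randomised difference is the direct estimate for that comparison, and two one-sample intervals do not say how large a difference remains possible. If the SAP had left it out, its precedence clause could be read as removing a planned analysis without declaring it.

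Even if the analysis is kept, Clopper-Pearson is a one-proportion method and cannot give the interval for a difference. A method chosen after the data are seen could make the result look more or less precise, most of all when nearly everyone responds.

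**Working it through.** **Step 1: is the analysis still planned?**

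- Protocol 9.4 includes the difference with a 95% interval.
- SAP 2.8 says nothing in the protocol's analysis has changed.
- The precedence clause in SAP 2.1 applies where the documents differ. Per-group intervals and a between-group difference can both be reported, so silence on the second does not contradict it.
- SAP 2.4.4 opens with an item (i) for the evaluative objective and shows no item (ii); a redaction follows. Protocol 2.1 lists the comparative objective directly after the evaluative one. The SAP contents also show redacted entries between 1.2.2 and 1.2.4 and between 2.4.4 and 2.4.6.

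The readable text therefore keeps the analysis, and its absence from the visible SAP cannot be held against the plan.

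**Step 2: what is left open?** SAP 2.4.2 fixes the missing-data rules: baseline observation carried forward in ITT for Month 9 GDS, and observed cases in ITT for the other effectiveness endpoints. Level and sidedness are also fixed. The interval formula, and whether it is stratified, are not readable.

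**Step 3: how much does the formula matter?** The documents give no expected responder rates and no figure to reproduce. About 30 subjects randomised 1:1 gives n = 15 per arm; the responder counts below are assumptions.

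Formulas, with z = 1.96 and p1, p2 the two rates:

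- Wald: (p1 − p2) ± z·√[p1(1 − p1)/n + p2(1 − p2)/n].
- Newcombe: with Wilson limits (l, u) for each arm, lower limit (p1 − p2) − √[(p1 − l1)² + (u2 − p2)²] and upper limit (p1 − p2) + √[(u1 − p1)² + (p2 − l2)²].
- Miettinen-Nurminen: the values of the difference not rejected by a score test with variance factor 2n/(2n − 1) = 30/29.

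Worked case, 12/15 in both arms. The Wilson limits are 0.548 and 0.930. The Newcombe half-width is √[(0.800 − 0.548)² + (0.930 − 0.800)²] = 28.3 points. The Wald half-width is 1.96·√(2 × 0.8 × 0.2/15) = 28.6 points. The Clopper-Pearson interval in each arm is 51.9% to 95.7%.

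Half-widths in points for equal arms:

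| Responders per arm | Newcombe | Miettinen-Nurminen | Wald |
|---|---|---|---|
| 9/15 | 31.5 | 33.8 | 35.1 |
| 12/15 | 28.3 | 30.1 | 28.6 |
| 13/15 | 26.4 | 27.9 | 24.3 |
| 14/15 | 23.8 | 24.9 | 17.9 |
| 15/15 | 20.4 | 20.9 | 0 |

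Unequal arms, 14/15 against 12/15 (difference 13.3 points): Newcombe −13.2 to 39.1, Miettinen-Nurminen −14.0 to 40.5, Wald −10.5 to 37.2. No limit moves by more than 3.5 points.

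The two score-type methods differ by at most 33.8 − 31.5 = 2.3 points in the table. Wald departs materially only near 100% response: 23.8 − 17.9 = 5.9 points narrower than Newcombe at 14/15, and zero width at 15/15.

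**The case for a change.** The best case for a change is that reading section 2.8 literally settles whether the difference is kept but not how it is computed, and naming a method would cost a sentence. The choice can also decide whether an interval covers zero. For 15/15 against 11/15, the continuity-corrected Wald interval is −2.4 to 55.7, while Newcombe gives 0.9 to 52.0 and Miettinen-Nurminen 3.0 to 52.4. For 14/15 against 9/15 the corrected Wald is −1.2 to 67.8, against 2.6 to 58.2 and 2.9 to 59.8. The protocol synopsis is uneven too: its statistical paragraph gives responder rates with intervals and does not mention the difference.

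The arithmetic stands, and so does the point that no readable text names a method. The consequence does not follow. These reversals need the continuity-corrected Wald, as the zero-width case needs the plain Wald, and neither is named anywhere readable. No readable margin, success criterion or stopping rule depends on whether zero is covered. The synopsis is a summary; section 9.4 is explicit. A method may already be stated in the redacted text, and the reported counts let any reader compute the interval.

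**Conclusion.** No change to the plan. Protocol 9.4 together with SAP 2.8 keeps the between-group difference, and the redactions rule out a finding that the SAP omits it. The remaining gap is the interval formula for a descriptive contrast in an open-label pilot whose primary objective is non-comparative and whose sample size is stated not to come from a calculation. An analyst facing about 15 per arm and possibly high response would be expected to use a score-type interval. Among the equal-count cases shown, choosing between the two common ones moves the half-width by at most 2.3 points. By either method the interval stays wide, around ±28 to ±30 points at 12/15 in both arms, and could not support a claim that the two volumes are equivalent.

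This rests on assumed responder counts, on 15 subjects per arm, and on taking the no-change statement in SAP 2.8 at face value.

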#### 2.4.4 Secondary Effectiveness Analysis

- (i) To evaluate the effectiveness of *Sculptra* for correction of wrinkles in the décolletage area, the following will be presented.

[figure not shown]
The percentage of responders on the GDS as assessed live by the Treating Investigator at 6 months after baseline will be presented along with the 95% confidence intervals (calculated via Clopper-Pearson) for each treatment group and overall.

The response rates based on the GAIS as assessed by the investigator and the subject, respectively, at each visit will be calculated and presented along with their 95% confidence intervals (calculated via Clopper-Pearson) for each treatment group and overall. A bar plot of the percentage of responders (at least “Improved”) by visit also will be produced for each evaluator type (investigator and subject) and presented by treatment group and overall. For the GAIS, response rate is defined as a subject with a rating of at least “improved”.

CCI

 GALDERMA EST. 1981	Title 43USSA2112 Statistical Analysis Plan - Sculptra Decolletage US Pilot	Doc id MA-55694
---	--	---------------------------

#### 2.4.6 Subgroup Analyses

All data will be summarized by treatment group injection volume: 8 vs 17 mL.

### 2.5 Safety Analysis

Safety endpoints will be summarized using descriptive statistics by treatment group based on the Safety population using observed cases. There are no planned inferential statistical analyses of safety endpoints.

#### 2.5.1 Treatment Administration, Post-injection Care, and Procedural Anesthetics

Treatment administration endpoints will be summarized for each treatment session by treatment group and overall, including injection technique, depth of injection, needle size, needle brand, and number of needles, vials, and syringes.

The number of subjects with any post-injection care and procedural anesthetics will be summarized by type.

Injection volume will be summarized for each treatment session and overall.

#### 2.5.2 Adverse Events (AEs)

All AEs will be coded according to MedDRA and summarized by System Organ Class (SOC), Preferred Term (PT), and treatment. The number of subjects with at least one event, associated percentage, and number of events will be provided.

GALDERMA <small>EST. 1981</small>	Title 43USSA2112 Statistical Analysis Plan - Sculptra Decolletage US PiLot	Doc id MA-55694
---	---	----------------------------------

Effective date: 2023-03-06 14:53

For subject counts, a subject will only be counted once per SOC and once per PT in cases where multiple events are reported for a subject within SOC or PT. For event counts, subjects with multiple events in a category will be counted for each event.

The number of subjects with AEs related to study product or study product injection procedure and unrelated AEs will be presented by SOC, PT, and maximum intensity. Action taken for related AEs will also be summarized by SOC and PT using number of events. AEs related to study product or injection procedure with late onset (> 21 days after most recent treatment session) will be listed.

Serious AEs and AEs of special interest (AESIs) will be listed. **CCI**

For AEs related to study product or study product injection procedure, the number of days to onset and the duration of event will be summarized by SOC and PT using mean, standard deviation, median, minimum, and maximum. Days to onset of an AE will be derived as the start date minus the date of most recent treatment session. Duration of an AE will be derived as the stop date minus the start date + 1. Missing stop date will not be imputed, and therefore no duration will be calculated in these cases.

In addition, a summary of all AEs will be provided, which will include (but is not limited to):

- number of subjects with at least one AE and number of events (in total as well as serious AEs),
- number of subjects with at least one related AE and number of events (in total as well as serious AEs),
- number of subjects with at least one AESI and number of events,
- number of subjects with at least one unrelated AE and number of events (in total as well as serious AEs),
- number of subjects who did not have an AE.

[figure not shown]

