2.2 Safety objectives and endpoints

Safety objective:

To evaluate the safety of *Sculptra* for correction of wrinkles in the décolletage area. Safety endpoints:

- 1. Incidence, intensity, time to onset and duration of Adverse Events (AE)s collected throughout the study period.
- 2. Incidence, intensity, time to onset and number of days of pre-defined expected post-treatment events collected using subject diaries for 28 days from each treatment.

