3.6.1 Emergency unblinding

Not applicable as the treating Investigator is not blinded to treatment.

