7. SAFETY ASSESSMENTS

Safety assessments for this study include:

- An evaluation and an interview of the subjects at each visit to obtain information about any
 medical occurrence that meets the definition of an AE
- Subject diary
- Laboratory assessment

Information on AEs can also be obtained from signs and symptoms detected during each examination by the Investigator or designee, which should include visual inspection of the treatment area.

AEs must be documented in the source document and eCRF without regard for cause or relation to the investigational device. Events that occur after Screening, but prior to randomization, should be recorded in the subject's medical history.

It is the responsibility of the Treating Investigator to determine the severity of the AE and relatedness of the event to the study device and/or injection procedures. AEs must be reported as outlined in Section 7.8.

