7.6 Adverse events

7.6.1 Definition of an Adverse Event (AE)

An AE is any untoward medical occurrence, unintended disease or injury, or untoward clinical signs (including abnormal laboratory findings) in subjects, users or other persons^a, whether or not related to the study product.

This definition includes:

- a) events related to the investigational product or the reference product
- b) events related to the procedures involved

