9.5 Safety analysis

The number and percentage of subjects reporting each pre-defined, expected, post-treatment symptom, as collected in the 28-day diary, will be presented in total and by maximum intensity. Number of days with the event will be presented by treatment group and category: 1, 2-7, 8-14, and 15-28 days.

All AEs will be coded according to medical dictionary for regulatory activities (MedDRA) and summarized by system organ class (SOC), preferred term (PT) and treatment.

AEs related to the study device or injection procedure and unrelated AEs will be presented by maximum intensity, SOC and PT. For related AEs, the number of days to onset and the duration of the event will be summarized by SOC and PT using mean, SD, min, max and median. Action taken for related AEs will also be summarized by SOC and PT. Serious AEs will be listed. To evaluate consistency of AEs across different subgroups, AEs will also be summarized by treatment group injection volume: 8 vs 17 mL.

In addition, a summary of all AEs will be provided, which will include (but is not limited to):

- number of subjects with at least one AE and number of events (in total as well as SAEs)
- number of subjects with at least one related AE and number of events (in total as well as SAEs)
- number of subjects with at least one un-related AE and number of events (in total as well as SAEs)
- number of subjects who did not have an AE

Handling of missing data 9.6

The number of missing values will be summarized and reported as appropriate. For the ITT analysis of the Treating Investigator GDS Responder rate at Month 9 after baseline (primary endpoint), missing values will be assumed to be missing due to lack of effect. Therefore, the primary method of imputation will use the baseline observation carried forward (BOCF) method. Impact of missing data on the primary endpoint will be evaluated by performing sensitivity analysis based on the observed cases, as well as worst-case and best-case imputation in the ITT set.

All other effectiveness endpoints will be evaluated based on the observed cases in ITT.

Descriptive statistics of all safety data will be performed on observed cases in the Safety population

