### 1.2.4 Safety Objectives and Endpoints

The safety objectives and endpoints are as follows:

- To evaluate the incidence, intensity, time to onset, and duration of adverse events (AEs) collected throughout the study period.
- Incidence, intensity, time to onset and number of days of pre-defined expected post-treatment events collected using subject diaries for 28 days from each treatment.

GALDERMA <small>EST. 1981</small>	Title 43USSA2112 Statistical Analysis Plan - Sculptra Decolletage US PiLot	Doc id MA-55694
---	---	----------------------------------

Effective date: 2023-03-06 14:53

*Effective*

Version: 1.0

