## 2.8 Changes in the Analysis Planned in the Protocol

There are no changes to the analysis planned in the protocol.

GALDERMA EST. 1981	Title 43USSA2112 Statistical Analysis Plan - Sculptra Decolletage US Pilot	Doc id MA-55694
------------------------------	---	----------------------------------

2023-03-06 14:53

Effective date:

*Effective*

Version: 1.0

GALDERMA EST. 1981	Title 43USSA2112 Statistical Analysis Plan - Sculptra Decolletage US Pilot	Doc id MA-55694
------------------------------	--	---------------------------

CCI

2023-03-06 14:53

Effective date:

*Effective*

Version: 1.0

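### Onset and duration are safety-endpoint components for all AEs, but both documents tabulate them only for AEs that the unblinded investigator judges related

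*SAP*

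**What the plan says.** Protocol 2.2 gives the first safety endpoint as "Incidence, intensity, time to onset and duration of Adverse Events (AE)s collected throughout the study period". SAP 1.2.4 repeats it: "To evaluate the incidence, intensity, time to onset, and duration of adverse events (AEs) collected throughout the study period". Neither sentence mentions causality, and Protocol 7.6.1 defines an AE as an untoward occurrence "whether or not related to the study product".

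The analysis sections are narrower for two of the four components. Protocol 9.5 states: "For related AEs, the number of days to onset and the duration of the event will be summarized by SOC and PT". SAP 2.5.2 carries this over, opening the relevant sentence with "For AEs related to study product or study product injection procedure, the number of days to onset and the duration of event". SAP 2.5.2 also lists late-onset events, meaning those starting more than 21 days after the most recent session, again only if related. SAP 2.8 states: "There are no changes to the analysis planned in the protocol". On this point that is correct, because the restriction starts in the protocol.

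On who decides relatedness, Protocol 7 says: "It is the responsibility of the Treating Investigator to determine the severity of the AE and relatedness of the event". Protocol 3.6.1 says of emergency unblinding: "Not applicable as the treating Investigator is not blinded to treatment".

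**The concern.** An endpoint defined on all AEs should have a summary on all AEs. Here an AE judged unrelated contributes to the incidence and intensity tables but to no specified table of onset or duration.

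The selecting variable also deserves care. Relatedness is an opinion formed by someone who knows whether 8 or 17 mL was used, and timing after injection plausibly informs that opinion. If it does, selecting on relatedness before summarising onset partly selects on the quantity being summarised. If the opinion also differs by arm, the two onset and duration tables can differ with no difference in what subjects experienced.

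This matters because Protocol 1.1 asks whether the larger volume is well tolerated, and Protocol 1.2 says the data will support a pivotal study.

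**Working it through.** The documents give no onset or duration figure, so there is nothing to reproduce. The main check is a comparison of the text.

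**Endpoint against analysis, by component**

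| Component | Endpoint (Protocol 2.2, SAP 1.2.4) | Specified summary (Protocol 9.5, SAP 2.5.2) |
|---|---|---|
| Incidence | AEs, no causality limit | All AEs by SOC, PT and treatment |
| Intensity | AEs, no causality limit | Maximum intensity, related and unrelated |
| Time to onset | AEs, no causality limit | Related only |
| Duration | AEs, no causality limit | Related only |

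Two of four components are tabulated for a subset. This needs no assumption.

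**Can the filter move the onset summary?** The following is illustration only. The share of AEs called related, and how it varies with timing, is not in the documents.

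Assume onset on days d = 0 to 42 with weight proportional to exp(−d/20). The weights and mean onsets in three bands are:

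- days 0–7: weight 0.373, mean 3.24 days
- days 8–21: weight 0.382, mean 13.69 days
- days 22–42: weight 0.245, mean 30.20 days

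Mean onset for all events = 0.373×3.24 + 0.382×13.69 + 0.245×30.20 = 13.8 days, with 24.5% after day 21.

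Let p₁, p₂, p₃ be the probabilities of being called related in the three bands. The share kept is Σwᵢpᵢ, and mean onset among related events is Σwᵢpᵢmᵢ / Σwᵢpᵢ.

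| p₁ / p₂ / p₃ | Share kept | Mean onset, related | Related with onset after day 21 |
|---|---|---|---|
| 95 / 95 / 95% | 0.95 | 13.8 d | 24.5% |
| 95 / 90 / 90% | 0.92 | 13.6 d | 24.0% |
| 95 / 80 / 60% | 0.81 | 12.1 d | 18.2% |
| 95 / 50 / 20% | 0.59 | 8.8 d | 8.2% |

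For the third row, the share kept is 0.354 + 0.306 + 0.147 = 0.807, and the mean is (0.354×3.24 + 0.306×13.69 + 0.147×30.20)/0.807 = 12.1 days.

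The shift runs from zero to five days and is set entirely by the assumed p values.

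**Is any such shift a bias?** A second illustration adds background illness. Follow-up is 252 days (9 months of 28 days), with four sessions 28 days apart and onset counted from the most recent session. Half of the AEs are background with uniform onset, and half are device-caused with exponential onset. Median days to onset:

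| Assumed attribution | All AEs | Related AEs |
|---|---|---|
| Independent of onset (50% called related) | 15.8 | 15.8 |
| Favours early events (device mean 14 d, 90% called related; background 50% up to day 21, 10% after) | 15.8 | 9.5 |
| Fully correct, device mean 7 d | 11.4 | 4.7 |
| Fully correct, device mean 90 d | 27.7 | 24.0 |

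In the last two rows the related-only figure is earlier although every label is right. That gap is the removal of background events, which is what a related-only table is for. An earlier onset among related AEs is therefore not in itself evidence of distorted labelling.

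**The case against.** Two stronger readings are tempting, and the documents support neither.

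A reader might infer that the endpoint is not delivered at all. In fact incidence covers all AEs, maximum intensity covers related and unrelated AEs, and onset and duration are tabulated for related AEs. Serious AEs and AESIs are listed without a causality filter. Start and stop dates are recorded for every AE (Protocol 7.7), and SAP 2.1.2 puts eCRF data and derived variables into subject listings. With about 30 subjects those listings can be read. Diary symptoms over 28 days after each session are summarised by number of days and plotted by day with no causality filter (SAP 2.5.3). This stands, with limits: a listing is not a summary by arm, and Protocol 7.2 displays diary data separately from AEs.

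A reader might also infer that onset is skewed early. Nothing in the documents shows that attribution depends on timing or arm, and the first illustration only returns what was assumed. The bar for relatedness is low: a reasonable possibility for either device or procedure suffices (Protocol 7.7.2). The sponsor also assesses causality, although no specified table uses that assessment.

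It can further be said that related-only is a coherent prespecified choice, since days from injection to an unrelated cold say little about the device. That justifies keeping the related-only table but does not reconcile it with an endpoint defined on all AEs. The general sentence in SAP 2.5, that safety endpoints are summarised by treatment group, specifies no further onset or duration table.

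Table formats sit in a companion document, and text after the AESI sentence in SAP 2.5.2 is redacted. The statement here is therefore about what the visible plan specifies.

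**Conclusion.** The mismatch is real and lies in both documents. Time to onset and duration are endpoint components for AEs regardless of causality, but they are specified for tabulation only among AEs judged related by an investigator who knows the arm. The endpoint is partly tabulated, and the late-onset listing shares the filter.

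That labelling may shift these tables, or make them differ by arm, is a possibility and not a finding. Its size cannot be estimated from the documents. Under assumed inputs it ranges from none to several days, and part of any shift would be legitimate. The primary effectiveness analysis is unaffected. The point is worth acting on because the correction uses data already collected and costs very little.

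**What to change.** In SAP 2.5.2:

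1. Keep the related-only onset and duration table.
2. Add the same table by treatment group for all AEs, regardless of causality.
3. Add it again for AEs whose recorded affected area (Protocol 7.7, item b) is the treatment area, regardless of causality. This selects on location instead of opinion and leaves out most intercurrent illness.
4. Apply the treated-area rule to the late-onset listing, so that a treated-area event more than 21 days after the most recent session appears whether or not it was called related.
5. Record the additions in SAP 2.8, since they go beyond Protocol 9.5.

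Rewording the endpoint in Protocol 2.2 and SAP 1.2.4 to related AEs would also remove the contradiction, but it would leave onset and duration resting wholly on arm-aware attribution.

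The cost is a SAP wording change and one or two more runs of an existing table, with no new data. The all-AE table will contain intercurrent illnesses. The visible text does not show affected area coded as treated area yes or no, so a mapping may have to be agreed before database lock.
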